6.1.7 Handling of Dropouts or Missing Data

Every effort will be made to minimize missing data for this study. The participant reported outcomes will be completed by the participant's primary caregiver on electronic devices. These assessments have been set up in such a way that the caregiver cannot proceed to the next question if they have not entered a response for the current question. In addition, on the off chance that the device does not function correctly, wherever possible, alternative data collection methods will be

utilized.

6.1.8 Pooling of Sites

As there are expected to be relatively few participants per centre, the centre will not be taken into account in the analyses. Therefore the question of pooling of centres does not arise.

6.1.9 Derived Variables

6.1.9.1 Adverse events

All AEs and serious adverse events (SAEs) will be collected from the start of intervention until the safety follow-up visit, with the following exception: all SAEs that occur after the consent form is signed but before study intervention is initiated must be reported by the investigator if they cause the participant to be excluded from the study or are the result of a protocol-specified intervention.

An AE will be considered treatment-related if the plausibility relationship to study intervention is recorded on the CRF as 'yes'. If the data on plausibility relationship to study intervention is missing, then the relationship will be set to missing, i.e., no imputation will be made. Events that start before the first dose of study intervention (pre-treatment) should be considered as not causally related unless the pre-treatment AE is reported to worsen post-treatment, in which case causality should not be ruled out.

An AE will be considered leading to permanent discontinuation of IMP if the action taken with study intervention is recorded on the CRF as 'DRUG WITHDRAWN' or the outcome is recorded on the CRF as 'FATAL'.

An AE will be considered leading to study intervention temporary discontinuation if the action taken with IMP is recorded on the CRF as 'DRUG INTERRUPTED'.

An AE will be considered leading to temporary or permanent study intervention dose reduction if the action taken with IMP is recorded on the CRF as 'DOSE REDUCED'.

An AE will be considered fatal if the outcome is recorded on the CRF as 'FATAL'.

The time to first onset of AE will be calculated as:

Start date of AE – Date of first dose of study intervention + 1

The time to AE resolution will be calculated for as:

Stop date of AE – Start date of AE + 1

6.1.9.2 Prior and concomitant medications

Medications that started and stopped prior to Day 1 will be considered prior medications. A concomitant medication is defined as any medication that was administered during the treatment period. This includes medications that started before the treatment period and continued while on treatment and medications that started during the treatment period.

There will be no imputation of partially or completely missing start/stop dates.

6.1.9.3 Age

Age will be recorded in months in the eCRF.

6.1.9.4 Exposure

The total number of dosing days in the treatment phase will be calculated as:

- (Date of last dose in the treatment phase from eCRF study outcome – Date of Day 1) + 1

The number of days in which study intervention was taken at least once (AM or PM) will be summarized and calculated as:

- Total number of dosing days – the number of days where study intervention was not taken in the AM nor PM (from morning/evening diary)

The number of days in which study intervention was taken both AM and PM will be summarized and calculated as:

- Total number of dosing days – the number of days with any missed doses

Compliance is calculated based on diary data, and recorded in eCRF:

- $100 \times [(Number\ of\ days\ study\ intervention\ taken\ at\ least\ once\ +\ number\ of\ days\ study\ intervention\ taken\ both\ AM\ and\ PM) \div (2 \times study\ day\ of\ completion\ or\ withdrawal\ during\ the\ treatment\ period)]$

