#### **8.5. Compliance in Study Intervention Administration**

The caregiver will record the volume of study intervention taken each morning and evening on each treatment day in the participant diary (refer to [Section 9.1.12.2](#) for additional information).

Caregivers should return all study intervention (unused, partially used, and empty containers) at each visit. The diary-reported dosing information will be checked and any discrepancies discussed with the caregiver at the time of the visit and documented accordingly within the participant's source documents.

Records of study intervention accountability will be maintained according to [Section 5.1.4](#).

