### **10.1. Discontinuation of Study Intervention**

- Parent(s)/LAR may decline to continue participating in study intervention and/or other protocol-required therapies or procedures at any time during the study.
- Parent(s)/LAR who choose to discontinue participating in study intervention and/or other protocol-required therapies or procedures should not be automatically removed from the study. Whenever safe and feasible, and in agreement with the sponsor, the participants should remain in the study to ensure safety surveillance and/or collection of outcome data.
- The investigator is to discuss with the participant's parent(s)/LAR the appropriate processes for discontinuation from study intervention or other protocol-required therapies. The investigator must discuss with the participant's parent(s)/LAR the possibilities for continuation of activities described in the SoA ([APPENDIX 1](#)) and must document this decision in the eCRF.
- These participants should complete an ET visit followed by 10-day taper period if clinically indicated (i.e., if no safety reasons prohibit continued treatment; refer to [Section 8.1.2](#)). A safety follow-up visit should be conducted 4 weeks after the participant's last dose of GWP42003-P. Remaining assessment visits and activities as determined by the investigator can still proceed as planned.

Reasons for removal from study intervention or procedural assessments include any of the following:

- Decision by the investigator.
- Decision by sponsor.
- Decision by regulatory authority.
- Withdrawal of parent(s)/LAR consent.
- Change in compliance with any inclusion/exclusion criterion that is clinically relevant and affects participant safety, as determined by the investigator (or designee).
- Protocol deviation that is considered to potentially compromise the safety of the participant.

- Noncompliance with study intervention.
- Noncompliance with any of the study assessments.
- Any clinically relevant sign or symptom that in the opinion of the investigator (or designee) warrants participant removal from study intervention.
- Liver Chemistry – Discontinuation of study intervention for abnormal liver tests is required by the investigator when a participant meets one of the following conditions outlined or in the presence of abnormal liver chemistries not meeting protocol-specified stopping rules if the investigator believes that it is in best interest of the participant.

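### SAP 6.1.9.4 counts doses to the last dose but days to withdrawal, which understates compliance for participants who stop dosing before withdrawing; days with no diary entry are separately credited as fully dosed

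*SAP*

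**What the plan says.** SAP 6.1.9.4 defines the total number of dosing days as "Date of last dose in the treatment phase from eCRF study outcome – Date of Day 1) + 1". Days with at least one dose are that total less "the number of days where study intervention was not taken in the AM nor PM (from morning/evening diary". Days with both doses are "Total number of dosing days – the number of days with any missed doses". Compliance is 100 times the sum of these two counts, divided by twice the study day on which the participant completed or withdrew in the treatment period. The source is stated as follows: "Compliance is calculated based on diary data, and recorded in eCRF".

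The surrounding text matters in three places:

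- **End dates.** SAP 6.1.4 sets the treatment period as Day 1 to Day 365. SAP 7.1 lists the date of completion or withdrawal, the date of last dose and the date of permanent treatment discontinuation as separate items. Protocol 10.1 says that, when drug is stopped, "the participants should remain in the study to ensure safety surveillance", where safe and feasible and with the sponsor's agreement. SAP 3.1 places the early termination visit after discontinuation.
- **What the diary holds.** SAP 7.4 describes a diary that captures doses departing from the schedule. Protocol 8.5 says: "The caregiver will record the volume of study intervention taken each morning and evening on each treatment day in the participant diary". Protocol 9.1.12.2 also has dose time and volume entered in a daily diary.
- **Missing entries.** SAP 6.1.7 describes how missing data are to be prevented. It gives no rule for a day with no dosing entry.

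**The concern.** The numerator and the denominator stop on different dates. A participant who took every dose until treatment ended, and was withdrawn from the study some days later, is charged with two missed doses for each day in between, when none was due. The listing would then show as poor adherence what is really early discontinuation.

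The numerator has a second weakness that works the other way. Because it starts from the calendar and subtracts recorded misses, a day on which nothing was entered subtracts nothing and is credited in full. Under the diary described in SAP 7.4 that is the intended meaning of a blank. Under the diary described in Protocol 8.5 and 9.1.12.2, a blank means that dosing on that day is unknown.

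Protocol 13.6.5 requires exposure and compliance to be summarised, and SAP 7.4 lists them by participant. With few participants and no averaging, each percentage is read as it stands. SAP sections 1 and 9.6 give poor recruitment and retention as the reason for ending the study, so early stoppers, the group exposed to the denominator problem, are relevant here.

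**Working it through.** The documents state no compliance percentage, so there is no figure to reproduce. The scenarios below are assumed and are not trial data.

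**Inputs, from SAP 6.1.9.4.** D = total dosing days. W = study day of completion or withdrawal. n0 = days recorded with no dose. n1 = days recorded with one of two doses missed.

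**Formula.** Days with at least one dose = D − n0. Days with both doses = D − n0 − n1. Their sum is 2D − 2n0 − n1, the number of doses not recorded as missed. Compliance = 100 × (2D − 2n0 − n1) / (2W).

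**Check when the dates coincide.** D = W = 365, n0 = 10, n1 = 20 gives (730 − 20 − 20)/730 = 690/730 = 94.5%, the correct share of doses. The formula is sound in this case.

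**Denominator.** With no missed dose, compliance reduces to 100 × D/W. The true value is 100% throughout.

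| Last dose | W − D = 0 | 1 day | 7 days | 14 days | 28 days |
|---|---|---|---|---|---|
| Day 84 | 100.0% | 98.8% | 92.3% | 85.7% | 75.0% |
| Day 364 | 100.0% | 99.7% | 98.1% | 96.3% | 92.9% |

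For example, 84/(84 + 7) = 84/91 = 92.3%, and 84/(84 + 28) = 84/112 = 75.0%. The same gap costs more the earlier dosing stops: 7 days costs 7.7 points at Day 84 and 1.9 points at Day 364.

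**No-entry days.** Let b = days with no dosing entry. With D = W = 365 and no recorded misses, the SAP figure is 100.0% whatever b is. Counting only documented doses gives 100 × (365 − b)/365:

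- b = 18 (about 5%): 347/365 = 95.1%
- b = 36 (about 10%): 329/365 = 90.1%
- b = 91 (about 25%): 274/365 = 75.1%

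The true value lies between the documented figure and 100%. The overstatement is therefore between zero and b/D.

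**With recorded misses as well.** D = W = 364, b = 91, n0 = 27, n1 = 0. Blanks counted as taken: (364 − 27)/364 = 92.6%. Blanks counted as missed: (364 − 91 − 27)/364 = 67.6%. The interval is 91/364 = 25.0 points wide.

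**Both effects together.** Last dose Day 84, withdrawal Day 112, b = 21, no recorded misses. The SAP gives 84/112 = 75.0%. Documented doses over dosing days give 63/84 = 75.0%. The two effects cancel here by coincidence. In general, a plausible SAP figure does not show that either effect is absent.

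**The case against.** The best defence is that SAP 7.4 describes an exception diary, for which subtracting exceptions is coherent. Withdrawal during the treatment period might also be read as withdrawal from treatment, which would make W equal D. Several controls exist. Protocol 8.5 has diary dosing checked and discrepancies discussed and documented at visits. Protocol 5.1.4 has returned drug compared with diary usage. Protocol 9.1.12.2 has entries reviewed with caregivers. SAP 7.1, 7.4 and 9.5.5 list the relevant dates, the amounts dispensed and returned, and the morning and evening dosing entries, so a careful reader could see a gap.

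Much of this stands. The controls make unresolved blanks less likely, though they do not say how a remaining blank is counted. The alternative reading of withdrawal is possible, but the text does not establish it: a participant can stop drug, remain on study and withdraw later, all within Days 1 to 365.

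The objection also disposes of some stronger inferences. A reader might infer that the overstatement equals the share of blank days. That requires that no dose was given on any blank day, so it is only a ceiling. A reader might take the 75% diary-completion criterion in Protocol 6.1.6 as a tolerated gap in dosing records. It concerns seizure-diary entries at baseline, before any drug. And a reader might assume that families who leave blanks miss more doses, which the documents do not show.

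**Conclusion.** The denominator is misaligned. Compliance is understated by the factor D/W for any participant whose dosing stops before the recorded completion or withdrawal day, and is unaffected otherwise. Under the assumed gaps of 7 and 28 days after a last dose on Day 84, a fully dosed child shows 92.3% and 75.0%. How often such gaps occurred cannot be known from the documents.

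The no-entry point is smaller. As written, the formula credits these days as two doses, which can overstate compliance by at most their share of dosing days. Whether that is an error depends on which description of the diary is right, and the protocol and SAP differ.

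A reader might conclude that both features make every reported percentage wrong. The documents do not support that: each effect is conditional, and they run in opposite directions. Nor do they support a threat to the primary safety or PK results. Compliance is not an endpoint, does not define any analysis set in SAP section 5, and is only listed by participant. The consequence is limited to the reported compliance and exposure figures, chiefly for early stoppers.

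**What to change.** 1. In SAP 6.1.9.4, replace the denominator with 2 × total number of dosing days (Day 1 to last treatment-phase dose).
2. Reconcile the exception-style diary of SAP 7.4 with the daily dose recording of Protocol 8.5 and 9.1.12.2, and state what a day with no entry means.
3. List the number of no-entry days per participant beside compliance.
4. Show two figures per participant over the corrected denominator: documented doses only (lower bound) and all doses not recorded as missed (upper bound). Reporting only the documented figure would score unknown days as missed and bias the result the other way.
5. Show the two day counts, at least one dose and both doses, on the same two bases.

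The cost is a few sentences, a small derivation change and extra listing columns, with no new data. If the eCRF value already uses the current formula, the percentage should be derived afresh in programming. If the SAP is already final, the change can be reported as a deviation in the study report, as Protocol section 13 provides. Compliance will rise for early stoppers, and the lower bound will be below the present figure where diaries are incomplete and the dates coincide.

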6.1.9.5 Data Adjustments/Handling/Conventions

A pre-specified subset of collected data will be listed to support production of the synoptic CSR.

7. Study Participants and Demographics

7.1 Disposition of Participants and Withdrawals

Participants who failed screening and reasons for screen failure will be listed.

Among participants in the safety analysis set, participant disposition through the safety follow-up will be listed, indicating

- participant status - completed or withdrew, and date of completion or withdrawal, if withdrew, primary reason for withdrawal. The date of the last dose will also be listed
- whether participant continued to the taper period (Yes/No) and if not, reason for not continuing; if the participant entered the taper period, whether the participant completed or not, and if not, the reason for not completing.
- whether the participant entered the safety follow-up (Yes/No).

Among participants in the safety analysis set, participants who permanently discontinued treatment will be listed along with the date of and reason for permanent treatment discontinuation.

Membership to the analysis sets – Screening, Safety, and PK, will be shown in listings of disposition.

7.2 Protocol Deviations

Protocol deviations will be categorized into the type of deviation and whether important or non-important before database lock. All protocol deviations will be listed for the screening analysis set.

7.3 Demographics and Baseline Characteristics

7.3.1 Demographics

The following data will be listed for the for the safety analysis set, and the efficacy analysis set only if different from the safety analysis set:

- Age (months)
- Gender (Male, Female)
- Ethnicity (Hispanic or Latino, Not Hispanic or Latino, Unknown)
- Race (American Indian or Alaska Native, Asian, Black or African American, Native Hawaiian or Pacific Islander, White, Unknown or Not Reported)
- Weight at baseline (kg)
- Height at baseline (cm)
- Body mass index at baseline (kg/m²)
- Previous use of cannabis

7.3.2 Seizure History – Current and Past

Seizure history will include seizures no longer occurring and current seizures. The following data will be listed for participants in the safety analysis set:

- For seizures no longer occurring,
 - Type of seizure (Focal motor, Focal non-motor, Tonic-clonic, Tonic, Clonic, Atonic, Absence, Myoclonic, Infantile/Epileptic seizures, Focal seizures which evolve to bilateral generalized convulsive seizures, Other)
 - Onset date and Resolved date
 - Description
- For current seizures
 - Type of seizure (Focal motor, Focal non-motor, Tonic-clonic, Tonic, Clonic, Atonic, Absence, Myoclonic, Infantile/Epileptic seizures, Focal seizures which evolve to bilateral generalized convulsive seizures, Other)
 - Onset date and Resolved date
 - Description
 - Seizure duration (2 mins, 2-10 mins, 10+ mins, unknown)
 - Seizure frequency (integer-valued) and duration. Duration, with possible values of ‘per hour’, ‘per day’, ‘per week’, ‘per month’, ‘lifetime’.
 - Triggers (Fever, Water, Excitement, Tiredness, Other).

7.3.3 Neuroimaging History

The following data will be listed for participants in the safety analysis set:

- Neuroimaging type (MRI, CT Scan, Ultrasound, Other: specifics)
- Date of most recent neuroimaging
- Result (Normal/Abnormal)
- Details of findings if partial, diffuse or non-specific/incidental

7.3.4 EEG history (Non-video and Video)

The EEG history data will be listed for participants in the the safety analysis set:

- Type of EEG (Non-video or Video)
- Date Performed and duration
- EEG result (Normal, Abnormal (Epileptiform), Abnormal (Non-epileptiform only), or report not available)
- If Abnormal, additional features as captured in the CRF (e.g., focal spikes)
- Whether seizures were observed, and if yes, type of Seizure (Focal motor seizures, Focal Non-Motor Seizures, Tonic-Clonic, Tonic, Clonic, Atonic, Absence Seizures, Myoclonic, Infantile/epileptic spasms, Focal Seizures which evolve to Bilateral Generalized Convulsive, Other)

In addition to above, for video EEG (VEEG) the following will be listed:

- EEG Recording Time (Start and Stop Date, Start and Stop Time), included only in listings
- Total Number of Focal Motor Seizures: Awake with Impairment, Awake without Impairment, Asleep with Impairment, Asleep without Impairment
- Total Number of Focal to Bilateral Generalized Convulsive Seizures: Awake, Asleep
- Total Number of Tonic Seizures: Awake, Asleep
- Total Number of Clonic Seizures: Awake, Asleep
- Total Number of Tonic-Clonic Seizures: Awake, Asleep
- Total Number of Atonic Seizures: Awake, Asleep
- Total Number of Myoclonic Seizures: Awake, Asleep
- Total Number of Absence Seizures: Awake, Asleep
- Total Number of Focal Non-Motor Seizures: Awake with Impairment of Consciousness or Awareness, Awake without Impairment of Consciousness or Awareness, Asleep with Impairment of Consciousness or Awareness, Asleep without Impairment of Consciousness or Awareness
- Total Number of Infantile Spasms: Awake, Asleep
- Total Number of Other Seizures: Awake, Asleep
- Total Unevaluable Hours of EEG recording (Hours)
- Total Evaluable Hours of EEG recording (Hours)
- Total Awake Duration (Hours)
- Total Asleep Duration (Hours)
- Interictal epileptiform activity: Yes or No
- Slowing: Yes or No
- Sleep Spindles: Yes or No
- Vertex Waves: Yes or No
- PDR (in hertz)

7.3.5 Medical History

The medical and surgical history and current medical condition data will be listed for participants in the safety analysis set. All conditions and diagnoses on the 'medical history' CRF page will be coded using the latest version of the Medical Dictionary for Regulatory Activities (MedDRA v24 or later).

7.4 Exposure and Compliance

Study intervention is to be administered twice daily (morning and evening). The first dose will be taken on Day 1. The date of final dose in the treatment phase will be recorded on the CRF. The date of final dose, for participants who enter the taper period, will be recorded on the CRF at the end of taper visit. The date of last dose in the treatment phase will be obtained from the CRF at the end of treatment visit. Any doses of study intervention that were not taken according to the dosing schedule will be captured in the daily dosing diary, together with the amount of study intervention that was administered.

Total number of dosing days in the treatment phase, and the number of days in which study intervention was taken at least once (AM or PM), and both AM and PM will be listed for all participants in the safety analysis set.

In addition, the amount of study intervention dispensed, and the amount of study intervention returned as recorded on the participant supply accountability log, and the % of the overall compliance calculated according to the Section 6.1.9.4 will be listed for all participants in the safety analysis set.

8. Efficacy Analysis

Efficacy will not be evaluated for the synoptic CSR.

8.1 Efficacy Endpoints

Seizure-related endpoints from either seizure diary data or VEEG will neither be listed nor summarized. These include indication-specific seizure frequency, seizure types, total countable seizures, percent reduction in total countable seizures from baseline to post-baseline, number of seizure-free days, treatment responder status

8.2 Infant Toddler Quality of Life Questionnaire

Caregivers will be instructed on how to record and complete the ITQOL-SF47 scale by recording from 0 (worst health) to 100 (best health). The ITQOL-SF47 will be completed at the site by the caregiver on an iPAD.

ITQOL-SF47 questionnaire items will be listed at baseline and end of treatment. See APPENDIX 4 for details.

ITQOL-SF47 scale scores are assessed on a validated, age appropriate QoL scale. Scale scores will also be listed.

9. Safety and Tolerability Analysis

Unless specified otherwise, safety data will be listed for participants in the safety analysis set.

